QODD-1***						X***

* Call window for completing assessments is within 7 days after time-point. After 7 days, paper versions will be mailed.

** Survey renamed "Satisfaction Questionnaire"

*** Completed once, 3 months post-death of participant

Outcome data will be collected via:

Quality of Life Instruments

The Chronic Liver Disease Questionnaire (CLDQ)²⁹ is a 29-item self-report questionnaire addressing domains specific to patients with liver disease including: abdominal symptoms, fatigue, systemic symptoms, activity, emotional function, and worry. Items are scored on a Likert-type scale measuring frequency of symptoms within the timeframe of the 'last two weeks,' from 1 – All of the time to 7 – None of the time. Initially validated in adults with a variety of types and stages of liver disease, the CLDQ has shown the ability to detect differences between patients without cirrhosis, with early cirrhosis, and with advanced cirrhosis (based on Child's Pugh classification), has shown good concurrent validity when compared to clinical evidence of deterioration²⁹, and has the ability to detect significant improvement in health-related QOL between patients pre-liver transplant and post-transplant.³⁰ (**Appendix L**)

In addition to a liver disease-specific assessment, the EQ-5D-5L³¹ will be collected as a secondary outcome measurement. The EQ-5D-5L is a valid and reliable generic health survey questionnaire, with 5 items measuring dimensions of Mobility, Self-Care, Usual Activities, Pain/Discomfort, and Anxiety/Depression. The 5L version has 5 response categories ranging from absence of symptom to extreme experience of the symptom. The EQ-5D-5L has been evaluated in patients with chronic hepatic diseases and has shown good criterion-related and construct validity in liver transplant patients.³² Scalone et al. (2013) evaluated the 5L version compared to the 3L version in 1,088 adult patients with chronic hepatitis (HCV and HBV), cirrhosis, hepatic carcinoma, or a recent liver transplantation, finding the 5L version performed well with a reduction

in ceiling effect with a modest-low gain in discriminant validity and slightly higher convergent validity as compared to the 3L version.³³ (**Appendix M**)

Mood Instruments

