We will use PROMIS adult short forms to assess mood in study participants, specifically depression (**Appendix N**) and anxiety (**Appendix O**). Patient Reported Outcomes Measurement Information System (PROMIS) is a system of highly reliable, validated, precise measures of patient-reported health status for physical, mental, and social well-being.³⁴ PROMIS' measures can be used as primary or secondary endpoints in clinical studies of the effectiveness of treatment. The domains of depression and anxiety are measured through four targeted questions each on a 5-point Likert scale. The four items are selected from a full item bank to yield an accurate estimate at a targeted range of the measured domain. Evaluation of construct validity has been accomplished through the specification and testing of hypotheses about the relationship between the PROMIS domain scores, actual clinical status, and other relevant variables. A variety of statistical techniques have been employed to evaluate these hypotheses including mixed-effects models, regression analysis, and structural equation models. Evaluation of construct validity is based on the relationship between the PROMIS scores and other health and clinical measures, and by evaluating known groups' validity.

Hospital Utilization

Days admitted as an inpatient will be compared between the usual care and intervention arm. Admission date, discharge date, and length of stay for inpatient hospitalizations and ICU admissions will be obtained from the Research Derivative. Associated costs and days alive outside of hospital will also be compared between arms.

Survival

Survival rates will be compared between the control and intervention arm one year after study enrollment.

Physical Symptoms

Disease trajectory including diagnoses and physical symptoms (e.g., ascites, variceal bleeding, encephalopathy) will be compared across arms.

Liver Transplant Status

Listing of liver transplant status (deferred, listed, declined), change in MELD score, and the number of completed liver transplants will be compared across arms.

Satisfaction Instruments

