Quality of End-of-Life Care: Questionnaire for Patient, developed at the University of Washington was modified for the current study.³⁵ The original instrument is an 11-item self-report questionnaire designed for the patient to rate the clinician, doctor, or nurse practitioner on 11 elements measuring quality of care. Items are scored on a 10-point Likert-type scale with 0 = "Poor", 5 = "Very Good", and 10 = "Absolutely Perfect" with an option for Does Not Apply (NA). The study team has modified this original questionnaire to remove the "End-of-Life Care" title from the header (**Appendix P**).

Caregiver Instruments

The Quality of End-of-Life Care: Questionnaire for Patient was modified for use by the Caregiver. The study team modified questions to be applicable for caregiver rather than patient response. For example, altering item 2 from "Responsive to your emotional needs . . ." to "Responsive to the patient's emotional needs . . .". The study team has modified this original questionnaire to remove the "End-of-Life Care" title from the header (**Appendix Q**).

If patients die during study participation, caregivers will be asked to complete one questionnaire at 3-months post-death to gauge quality of end-of-life care. The Quality of Death and Dying (QODD-1) is a 1-item questionnaire that measures overall quality of dying with the question, “Overall, how would you rate the quality of your loved one’s dying?” Response options range from 0 – a “terrible” experience to 10 – an “almost perfect” experience. The QODD-1 has shown to correlate significantly with clinical variables associated with end-of-life care and palliative care.^{36,37} (**Appendix R**)

The Kingston Caregiver Stress Scale (KCSS)³⁸ will be used to measure caregiver stress. The KCSS is designed to measure stress experienced by lay caregivers, not institutional staff, and was designed to monitor change in an individual's stress over time. Ten items are grouped into three categories: care giving, family, and financial issues. (**Appendix S**)

Provider satisfaction

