Aim 1: Time to first hospital readmission within 1-year post randomization will be compared across treatment assignment using Cox proportional hazards model, accounting for the competing risk of death and adjusting for relevant demographic and clinical characteristics. A less than 1 hazard ratio for the treatment group status implies reduced readmission rates in the intervention arm given equal mortality rates.

Aim 2: Days alive out of hospital within 6-months post randomization, total days in hospital and ICU within 1-year post randomization, number and cost of hospital admissions within 1-year post randomization, median length of stay per admission, number of transfers to hospice within 1-year post randomization, time to hospice placement after referral, survival, presence of advance directives within 1-year post randomization, presence of physical symptoms, transplant status listing (deferred, listed, declined), and number of completed liver transplants will be obtained via chart review and compared across treatment assignment using proportional odds model for ordinal outcomes, Cox proportional hazards model for time-to-event outcome and logistic regression for binary outcomes, adjusting for relevant demographic and clinical characteristics.

Aims 3 and 4: Both cross-sectional and longitudinal analysis will be conducted to compare between group differences in CLDQ. For the cross-sectional study, for each time point of data collection, linear regression with ordinary least square will be used with CLDQ as the dependent variable (DV) and treatment assignment (0 for control arm and 1 for the intervention arm) as the independent variable (IV) of interest adjusting for baseline CLDQ and potential confounding factors based on clinical and statistical considerations. A positive value of the regression parameter for treatment status indicates higher CLDQ in the intervention arm. For longitudinal analysis, linear mixed model will be adopted including follow-up time and the interaction between follow-up time and treatment group on top of the cross-sectional model. The interaction term is included to compare decreasing rate of CLDQ between groups with a positive value of the corresponding regression parameter indicating slower decline rate of CLDQ in the intervention arm.

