The same series of analyses for the CLDQ will be conducted for the PROMIS (depression, anxiety), ED-5D-5L, the Quality of End-of-Life Care patient and caregiver questionnaires, and the KCSS. Histogram of baseline secondary outcomes will be used to evaluate ceiling/flooring effect and degree of skewedness. Appropriate transformation such as log transformation will be considered for highly skewed secondary outcomes to improve efficiency. A positive value of the main effect for intervention status in the cross-sectional analyses and a positive value of the interaction effect in the longitudinal analyses indicate favorable intervention effect.

Aim 5: Summary descriptive measures such as mean, quartiles and standard deviation for continuous variables and frequencies for categorical variables will be provided for process outcomes from participants in the intervention arm to evaluate fidelity of the proposed intervention and generalizability of implementing a large-scale intervention program. The following data will be collected for each arm: percentage of patients with answered surprise question (stratified by provider), percentage of patients with a 'No' response to the surprise question (stratified by provider), percentage of patients with 'No' response to the surprise question who were approved for study enrollment (stratified by provider), percentage of intervention patients who received initial PC inpatient consult, percentage of patients who received scheduled follow-up telephone contact, percentage of patients who attended an appointment for care after referral was obtained, percentage of patients with completed questionnaires at each time point, percentage of patients who received Palliative Care materials, and percentage of patients who received an inpatient PC consultation upon hospital readmission during the intervention phase will be calculated.

Interim Analysis

Interim analysis will be conducted when N=30 and N=150 participants are enrolled and followed for at least 6 months to evaluate whether the study is feasible, study procedures are conducted as intended, and that there is not significant patient dropout for mortality or other reasons.

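### The plan calls a positive treatment coefficient favourable for every questionnaire, which is backwards for PROMIS depression, PROMIS anxiety and the KCSS if higher scores mean worse

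*Combined protocol and SAP*

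**What the plan says.** Under Aims 3 and 4 in section 8.0 Statistical Analyses, the CLDQ is the template. A linear regression at each time point uses "treatment assignment (0 for control arm and 1 for the intervention arm) as the independent variable (IV) of interest", adjusted for baseline CLDQ and other factors. A positive treatment coefficient is read as a higher CLDQ in the intervention arm. A linear mixed model adds time and a time-by-treatment interaction, with "a positive value of the corresponding regression parameter indicating slower decline rate of CLDQ in the intervention arm".

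The next paragraph carries these models over: "The same series of analyses for the CLDQ will be conducted for the PROMIS (depression, anxiety), ED-5D-5L" (evidently the EQ-5D-5L), the patient and caregiver Quality of End-of-Life Care questionnaires, and the KCSS. It allows a log or similar transformation for highly skewed outcomes. It closes with one rule for all of them: a positive cross-sectional main effect and "a positive value of the interaction effect in the longitudinal analyses indicate favorable intervention effect".

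The instruments are described in section 7.2. CLDQ symptom items run "from 1 – All of the time to 7 – None of the time". The satisfaction items run from 0 at the poor end to 10 at the perfect end. For PROMIS, "The domains of depression and anxiety are measured through four targeted questions each on a 5-point Likert scale". The KCSS is described as a measure of stress in lay caregivers. For the EQ-5D-5L, "The 5L version has 5 response categories ranging from absence of symptom to extreme experience of the symptom".

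**The concern.** The sign rule is right for the CLDQ because a higher CLDQ means fewer symptoms. It is then applied unchanged to scales that measure something undesirable. With the intervention arm coded 1, a positive coefficient on a depression, anxiety or stress score that rises with severity means more depression, anxiety or stress in the palliative care arm, or faster worsening there. The plan would record that as a favourable effect, and a true improvement as an unfavourable one.

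The outcomes concerned are patient mood, a listed secondary outcome, and caregiver stress, which is named in Aim 4. Aim 4 shows the conflict most plainly. It pairs caregiver stress with caregiver satisfaction, and if each is scored in the direction of its name, the two cannot share one favourable sign.

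**Working it through.** The plan gives no figure to reproduce here. The check concerns direction.

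**Step 1: what a positive coefficient means.** With control = 0 and intervention = 1:

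- Cross-sectional model: the treatment coefficient is the adjusted mean score, intervention minus control. Positive means a higher score in the intervention arm.
- Mixed model: the interaction is the slope in the intervention arm minus the slope in the control arm. Positive means the score falls more slowly, or rises faster, in the intervention arm.

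Both are favourable if higher is better. Both are unfavourable if higher is worse.

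**Step 2: direction of each instrument, from section 7.2.**

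| Instrument | What the protocol gives | Does the rule hold? |
|---|---|---|
| CLDQ (template) | 1 to 7, higher = symptoms less often | Yes |
| Patient satisfaction | 0 to 10, higher = better | Yes |
| Caregiver satisfaction | Adapted from the patient form; same scale inferred | Yes |
| PROMIS depression | Measures depression; direction not printed | Reversed if higher = more depression |
| PROMIS anxiety | Measures anxiety; direction not printed | Reversed if higher = more anxiety |
| KCSS | Measures stress; direction not printed | Reversed if higher = more stress |
| EQ-5D-5L | Levels run from absence to extreme; analysed score not named | Cannot be settled |

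**Step 3: count over the six added instruments.** 2 (rule fits) + 3 (reversed if scored in their named direction) + 1 (EQ-5D-5L, open) = 6.

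- All four undetermined scores oriented higher = better: 0 of 6 reversed.
- PROMIS depression, PROMIS anxiety and KCSS in their named direction, EQ-5D-5L higher = better: 3 of 6.
- The same, with the EQ-5D-5L analysed as levels numbered upward from absence to extreme: 3 + 1 = 4 of 6.

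**Step 4: does anything in the plan repair the sign?** Only reversing the score would. The least-squares estimate is (X'X)⁻¹X'Y, so replacing Y by −Y changes every coefficient to its negative. The mixed-model estimate (X'V⁻¹X)⁻¹X'V⁻¹Y behaves in the same way, because the variance components do not depend on the sign of Y. Reversing the baseline score as well affects only the baseline coefficient. Standard errors and two-sided p-values stay as they were.

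No reversal is written. The only transformation named is a log, which keeps the order of scores. A simulated illustration (400 patients, 5 visits, a true benefit that lowers a higher = worse score; all effect sizes assumed) gave:

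| Score analysed | Treatment coefficient (one visit) | Time-by-treatment interaction |
|---|---|---|
| Higher = worse, as scored | −0.517 | −0.071 |
| Same data, reversed | +0.517 | +0.071 |
| Log of the shifted higher = worse score | −0.148 | −0.020 |

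A real benefit therefore appears as a negative coefficient, with or without the log. The mixed-model fits gave convergence warnings, so the interaction values are illustrative only. The sign result rests on the algebra.

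**Step 5: the protocol's own view of benefit.** Section 1.0 Background counts fewer depressive symptoms, and improvement in anxiety and depression, among the benefits reported for palliative care. A rule that treats higher depression or anxiety scores as favourable would contradict this.

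**The case against.** The strongest objection is that the error is conditional. Nothing in the text available for review states how PROMIS depression, PROMIS anxiety or the KCSS is scored. The forms are in Appendices N, O and S, which are not in that text and may show the direction. The closing sentence could also be read as a convention that scores will be oriented so that positive is favourable. The first part stands: direction has to remain an assumption, and the range has to start at 0 of 6. The second has no textual support, because no reversal step is written and the sentence directly follows a list of scales with differing orientations.

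Three smaller objections stand in part. The Background statements describe other studies; they show which way benefit lies for mood, not how this trial orients its scores, and they say nothing about caregiver stress. By its name as a quality-of-life measure, the EQ-5D-5L would be higher = better, so the 4 of 6 figure is an outer bound that depends on an unstated scoring choice. The 0 to 10 scale is printed for the patient questionnaire and only inferred for the caregiver version.

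It can also be said that an analyst would notice, and that no test, stopping rule or success criterion depends on the sentence. That limits the damage. But this is where the plan defines a favourable effect for these outcomes, so an analyst who ignores it departs from the plan without a written basis.

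**Conclusion.** The concern holds. On the natural reading of scales that measure depression, anxiety and stress, the rule is wrong as written for 3 of the 6 added instruments. This rests on two points: that higher scores on those three mean worse, which the available text does not confirm, and that no reverse-scoring precedes the analysis, since none is stated. If the scores are in fact to be reversed, the rule would be correct, but it depends on a step the statistical section omits; the section needs correcting either way. The unnamed EQ-5D-5L score is a separate gap, and the conclusion does not depend on it.

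The consequence is confined to interpreting secondary outcomes under Aims 3 and 4. The primary analysis is untouched. It should be fixed, because the plan could otherwise lead harm to be reported as benefit, or the reverse.

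**What to change.** Replace the closing sentence with a short list giving, for each instrument, the score analysed, its direction and the favourable sign:

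- CLDQ and both satisfaction questionnaires: positive.
- PROMIS depression, PROMIS anxiety and KCSS: negative, once it is confirmed that higher scores mean worse.
- EQ-5D-5L: name the score to be analysed and give its sign.

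Alternatively, pre-specify that the three scales are reverse-scored before analysis, so that positive is favourable throughout; the EQ-5D-5L score must still be named. Either way, the cost is a wording change in the statistical section. Data collection, models and sample size stay the same.

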8.0 Risks and Benefits and Means of Mitigating Risks

The benefits of this research are potentially quite large and the risks comparatively small. Specifically, this research may lead to a better understanding of the value of palliative care and its optimal timing for patients with life-threatening illnesses. It will also potentially yield important information about the impact of the time of such palliative care on the patients and their well-being. We believe the potential benefit to society of results of this study, if positive, may ultimately lead to different and improved clinical approaches to the care of such patients with life-threatening illnesses, most of whom could be considered to be at the end of life. The risks associated with this research relate to the potentially emotionally upsetting nature of some of the questions, including those related to estimating the likelihood of patients being cured of their life-threatening diseases and their likelihood of survival. Our preliminary data show that patients overwhelmingly want to know about this kind of information, but we will work to minimize risks to patients by forewarning them during the consent process about the potential emotional distress and refer patients to a trained social worker if necessary.

References

